2.2. Study Endpoint(s)

2.2.1. Efficacy Endpoint(s)

- (1) Primary efficacy endpoint
WOMAC pain subscale score (change from baseline at Week 16)
- (2) Key secondary efficacy endpoint
WOMAC physical function subscale score (change from baseline at Week 16)
- (3) Secondary efficacy endpoints
 - 1) Patient global assessment (PGA) (change from baseline at each assessment time point)
 - 2) WOMAC pain subscale score (change from baseline at each assessment time point)
 - 3) WOMAC physical function subscale score (change from baseline at each assessment time point)
 - 4) WOMAC stiffness subscale score (change from baseline at each assessment time point)
 - 5) WOMAC total score (change from baseline at each assessment time point)
 - 6) Proportions of subjects with 30%, 50%, 70% and 90% improvements in their WOMAC pain subscale scores compared to baseline (Weeks 16)
 - 7) Proportions of subjects with 30%, 50%, 70% and 90% improvements in their WOMAC physical function subscale scores compared to baseline (Weeks 16)

- 8) Numerical Rating Scale (NRS) score for the mean pain on walking in the evaluated joint (change from baseline at each assessment time point)
- 9) SF-36 (change from baseline at each assessment time point)
- 10) EQ-5D-5L (change from baseline at each assessment time point)
- 11) Improvement rate based on the Outcome Measures in Rheumatology Arthritis Clinical Trials-Osteoarthritis Research Society International (OMERACT-OARSI) criteria (at Weeks 16)
- 12) Amount of rescue medication used (number of days on which rescue medication was used, and amount [number of tablets] used)

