7.1.2.8. Rescue Medication

Baseline amount of rescue medication use is defined as the average of the non-missing values during 7 days prior to taking study drug. For each week, the average of the non-missing values during the 7 days on or prior to that week will be used.

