7.3. Data Handling Convention for Missing Data

(1) Non-PK related

Efficacy:

WOMAC

WOMAC scores will be computed when one pain, one stiffness, or 1-3 physical function items are missing. The missing items will be imputed by the mean of available items within the same subscale. The scores will be set to missing if more items are missing.

NRS

If all values are missing for the 7 days, the value for that week is set to missing.

SF-36 / EQ-5D-5L

- SF-36 subscale scores will be computed if at least 50% of items are available. The missing items will be imputed by the mean of available items.
- EQ-5D-5L index will be set to missing if any of the 5 dimensions is missing.

Adverse events:

If severity or relationship is found to be missing the most severe occurrence will be imputed for the summary of interest.

For AE start missing or partial dates, the AE will be treated as TEAE if it cannot be determined to be a non-TEAE.

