The SAS code planned for the analysis is outlined below.

[REDACTED]

[REDACTED]

[REDACTED]

[REDACTED]

[REDACTED]

[REDACTED]

Response rate based on the OMERACT-OARSI criteria at Week 16 compared to baseline

Responder analyses for OMERACT-OARSI will be summarized at each visit using the same GLMM approach in previous model.

Proportion subjects who used rescue medication

The proportion of subjects taking rescue medication in baseline and up to week 16 will be summarized by treatment group. Number of days on rescue medication during treatment period (Day 1 to Day 28, Day 29 to Day 56, Day 57 to Day 84, Day 85 to Day 112) will be summarized by treatment group. Number of weekly average usage of rescue medication will be summarized at each week by treatment group.

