A generalized linear mixed-effects model (GLMM) by logit type for response variable will be used to evaluate these binary response variables. The denominator degrees of freedom for the test statistics of estimated parameters will be approximated using the Kenward-Roger method. The estimated response rate for each treatment group and placebo group and 95% confidence interval of the odds ratio of each of the MT-5547 1 mg q4w and MT-5547 1 mg q8w groups compared to the placebo group in each binary response variables will be calculated using this GLMM approach.

- The covariates: baseline and the interaction of baseline and measurement time point.
- The fixed factors: Treatment group, measurement time point, the interaction of treatment group and measurement time point, K-L grade (2-3 or 4), and evaluated joint location (knee or hip)
- Random factors: Measurement time point for subject specific with covariance structure of unstructured

The sample SAS code planned for the analysis is outlined below.

[REDACTED]

Response rate based on the OMERACT-OARSI criteria at each assessment time point compared to baseline

Responder analyses for OMERACT-OARSI will be summarized at each assessment time point using the same GLMM approach in previous model.

Proportion subjects who used rescue medication

The proportion of subjects taking rescue medication in baseline and up to week 48 will be summarized by treatment group. The proportion of days on rescue medication use during treatment period will be summarized at each week by treatment group. Number of average usage of rescue medication will be summarized at each week by treatment group.

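### One of three rescue-medication summaries in the Week 16 SAP counts days of use per 28-day block with no denominator, so incomplete blocks are under-counted

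*SAP*

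**What the plan says.** The endpoint list in section 2.2.1 of the Week 16 SAP names rescue use as a two-part secondary endpoint: "Amount of rescue medication used (number of days on which rescue medication was used, and amount [number of tablets] used"). Section 8.2.3 then plans three summaries by treatment group, with no model or test.

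- Subjects using rescue: "The proportion of subjects taking rescue medication in baseline and up to week 16 will be summarized by treatment group".
- Days of use: "Number of days on rescue medication during treatment period", in blocks of Days 1-28, 29-56, 57-84 and 85-112.
- Weekly usage: "Number of weekly average usage of rescue medication will be summarized at each week by treatment group".

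Section 7.1.2.8 defines the weekly figure on observed data: "For each week, the average of the non-missing values during the 7 days on or prior to that week will be used". Nothing similar is given for the count of days. The missing-data rules in section 7.3 cover WOMAC, NRS, SF-36, EQ-5D-5L and adverse events, but not rescue use. The list of errata, as far as it is readable, does not change this.

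For the same endpoint, section 8.2.1 of the Week 68 SAP plans a proportion in place of the count: "The proportion of days on rescue medication use during treatment period will be summarized at each week by treatment group".

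**The concern.** The data come from a nightly diary. Protocol 9.2.2.3 has remaining drug collected and use checked at visits to Week 48 and at treatment discontinuation, and the post-treatment schedule shows no rescue entry. A patient who stops on, say, Day 98 can therefore contribute at most 14 of the 28 days in the last block, and the planned statistic does not adjust for that.

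If the arms lose patients at different rates, the count partly measures who stayed. Dropout for poor pain relief is a realistic prospect: insufficient efficacy is a listed discontinuation reason (Protocol 12.3), and naproxen is added for placebo patients to limit dropout, but only from Week 16, after these four blocks. Were placebo to lose more patients, its rescue use would look lower than it is and a rescue-sparing effect of MT-5547 would be partly hidden. In addition, the Week 16 and Week 68 reports would show the same first 16 weeks on different scales.

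**Working it through.** **The plan's own dropout figure.** No expected value is stated for rescue use. The only stated figure built on dropout is the original group size in SAP 3.3: 120 completers with 15% missing, 120 / (1 - 0.15) = 141.2, rounded up to 142. This reproduces, and it uses the same 15% in every arm.

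**Inputs.**

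- Block length 28 days, horizon 112 days: Week 16 SAP 8.2.3.
- Missing Week 16 pain data in the overseas phase 2/3 study: placebo 71 of 83 present, (83 - 71)/83 = 14.5% missing; 1 mg 75 of 85 present, (85 - 75)/85 = 11.8% missing (Table 3.3-1). The table note says these counts include data after treatment discontinuation, so they may understate treatment dropout.
- Assumed, not in the documents: true use on 60% of days in both arms; dropout spread evenly over 112 days and unrelated to use; the dropout pairs 18/10 and 15/10.

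**Formulas for Days 85-112.** Let d be cumulative dropout by Day 112. A share 0.75d has left before Day 85, and 0.25d leave during the block after 14 days on average. Full use is 28 × 0.6 = 16.8 days.

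- Patients already gone counted as zero: 16.8 × [(1 - d) + 0.25d/2] = 16.8 × (1 - 0.875d).
- Patients already gone excluded, partial counts kept: 16.8 × (1 - 0.875d) / (1 - 0.75d).

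| Dropout, placebo vs active | Gone excluded (days) | Gap | Gone counted as zero (days) | Gap |
|---|---|---|---|---|
| 18% vs 10% (assumed) | 16.36 vs 16.57 | 0.21 | 14.15 vs 15.33 | 1.18 |
| 15% vs 10% (assumed) | 16.45 vs 16.57 | 0.13 | 14.60 vs 15.33 | 0.74 |
| 14.5% vs 11.8% (overseas study) | 16.46 vs 16.53 | 0.07 | 14.67 vs 15.07 | 0.40 |
| 15% vs 15% (SAP assumption) | equal | 0 | equal | 0 |

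True use is equal in every row, so each gap is spurious and shows placebo using less. All figures scale in proportion to the assumed use rate.

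**Level within an arm.** Even with equal 15% dropout the count is low. Counting absent patients as zero, Days 1-28 read 16.8 × (1 - 0.15/8) = 16.5 and Days 85-112 read 14.6, an apparent fall of 1.9 days when use is constant.

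**Does a denominator help?** If dropout is unrelated to use, dividing by observed diary days removes the mechanical shortfall. If heavier users leave more often, it helps only in part. In a simulation with 50% true use in both arms (14 days per block), dropout of 20% placebo and 10% active, and each patient's chance of leaving proportional to that patient's own use, the placebo-minus-active bias in Days 85-112 was:

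- -0.52 day for the count with patients already gone excluded;
- -1.46 days for the count with them as zero;
- -0.25 day, per 28 days, for use divided by diary days observed.

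**The case against.** The tempting stronger reading is that the Week 16 SAP reports rescue use as a raw count and that the endpoint is therefore biased by differential dropout, by about 1.2 days. The documents do not support that.

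- The count is one of three summaries. The weekly average covers the amount of use and already rests on non-missing days, so missing days do not mechanically lower it.
- The 1.2-day figure needs an assumed 18% versus 10% dropout and a zero-counting rule the SAP does not contain. Its conventions lean the other way: section 6.1 reports the number of observations beside the number in the analysis set, and section 7.1.2.8 averages observed values. With absent patients excluded, the same inputs give 0.2 day.
- The design assumes equal missingness, at which the between-arm gap is zero. No document gives rescue use among patients who dropped out.
- Protocol 17.5 has blank diary entries filled in at visits as far as possible, which limits gaps within a block among patients still attending.
- The count is what the protocol names, so replacing it would drop the specified measure.
- The Week 68 SAP covers data from screening and reports a proportion of days, so a rate version is coming, though it does not spell out its denominator.

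All of this stands, and it limits the size and certainty of the problem. It does not supply the missing denominator or a rule for incomplete blocks in the Week 16 report.

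**Conclusion.** The point holds as a limited one. As written, the days-of-use summary under-counts any patient with an incomplete 28-day block, and it can distort the comparison between arms if dropout differs. Distortion is a possibility that depends on dropout and on handling not yet specified; it is not an established bias. Under the 60% use assumption, the plausible range for Days 85-112 runs from zero (equal dropout), through about 0.07 to 0.4 day (overseas study rates), to 0.2 or 1.2 days (assumed 18% versus 10%), the higher figure in each pair requiring absent patients to count as zero.

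If placebo loses more patients, the error understates placebo use and so works against the drug; it would not create a false benefit. The rescue summaries are descriptive and lie outside the four-hypothesis multiplicity procedure, so no confirmatory conclusion changes. This is a cheap improvement, not a flaw that threatens the trial.

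**What to change.** In section 8.2.3 of the Week 16 SAP, keep the protocol-named count and report beside it, for each 28-day block, days of rescue use divided by days with a diary entry. Set the value to missing for a patient with no diary days in that block, and show the number of patients contributing. State in section 7.3 how the plain count treats incomplete blocks. This matches the non-missing rule in section 7.1.2.8 and brings the report into line with the proportion of days in the Week 68 SAP, whose denominator should be defined in the same way.

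The cost is one derived variable from data already collected. If the Week 16 data are already locked, Protocol 13.4 allows an added analysis provided the reason is given and the result is kept distinct from those planned. The limitation to state is that bias from heavier users dropping out is reduced, not removed.

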8.3. Safety Assessments

Safety assessments will be made on the SAF population.

8.3.1. Adverse Events

Overall summary for the following will be conducted.

- Subjects with at least one TEAE
- Subjects with at least one adverse drug reaction
- Subjects with at least one TESAE
- Subjects with at least one serious adverse drug reaction
- Subjects with at least one AESI
- Subjects with at least one TEAE leading to discontinuation of study drug
- Subjects with TEAE leading to death

The following summaries also will be conducted.

- TEAEs by SOC and PT
- Adverse drug reactions by SOC and PT
- AESI by SOC and PT
- TESAEs by SOC and PT
- Serious adverse drug reactions by SOC and PT
- TEAEs leading to discontinuation of study drug by SOC and PT
- TEAEs by SOC, PT and severity
- Adverse drug reactions by SOC, PT and severity

Each of the summaries will be done by treatment group at the subject level - multiple occurrences of the same event within a subject will be counted once in the summaries by SOC and PT; multiple occurrences of the same event within a subject will be counted once in the

maximum severity category (severe > moderate > mild) and/or maximum drug relationship category (reasonable possibility/no reasonable possibility) and/or the earliest duration.

9. DATA PRESENTATION CONVENTIONS

9.1. Number of Digits to Report

(1) Non-PK related

Statistic	Specification	Apply to
Minimum, Maximum	Same number of DPs as the data provided in the datasets	All original (i.e. non-derived)
	see section 7.3	All derived data
Mean, Median, SD, SE, Confidence intervals	One more DP than above	All
Percentages ^{*1}	1 DP	All
Ratios	3 DPs	All
p-values ^{*2}	3 DPs	All

*¹ Percentages: use 1 place beyond the decimal point, except for the following cases:

If the percentage is equal to 0, then leave blank, do not use (0)

If the percentage is equal to 100, then use "(100)" without a decimal

*² p-values: use 3 places beyond the decimal point, except for the following cases:

If the p-value is less than 0.001, then use p<0.001

9.2. Treatments to Report

Treatment	For TFLs
MT-5547 1 mg q8w	MT-5547 1 mg q8w
MT-5547 1 mg q4w	MT-5547 1 mg q4w
MT-5547 1 mg q4w and MT-5547 1 mg q8w	MT-5547 Combined
MT-5547 3 mg q4w	MT-5547 3 mg q4w
MT-5547 6 mg q8w	MT-5547 6 mg q8w
Placebo	Placebo
Placebo group and all active dose levels	Total

9.3. Analysis Visits to Report

(1) Non-PK related

Efficacy:

Analysis Visit	Apply to			
	WOMAC and PGA	SF-36 and EQ-5D-5L	Weekly average NRS and Rescue	Daily NRS

			Medicine	
Baseline	X	X	X	X
Day 1				X
Day 2				X
Day 4				X
Day 6				X
Week 1	X		X	X
Week 2	X		X	X
Week 3			X	X
Week 4	X	X	X	X
Week 5			X	X
Week 6			X	X
Week 7			X	X
Week 8	X	X	X	X
Week 9			X	X
Week 10			X	X
Week 11			X	X
Week 12	X		X	X
Week 13			X	X
Week 14			X	X
Week 15			X	X
Week 16	X	X	X	X

10. CHANGE FROM THE PROTOCOL

There are currently no changes to analysis from protocol.

11. SOFTWARE

[figure not shown]
All statistical analyses will be performed using SAS version 9.3 or higher.

[figure not shown]

13. APPENDIX

[figure not shown]

FAS	full analysis set
K-L	Kellgren-Lawrence
LLOQ	lower limit of quantification
MAR	missing at random
MedDRA	medical dictionary for regulatory activities
MMRM	mixed effect model for repeated measures
NAb	neutralizing anti-drug antibody
NGF	nerve growth factor
NRS	numerical rating scale
NSAID	nonsteroidal anti-inflammatory drug
OA	osteoarthritis
██████████	██████████
OMERACT-OARSI	Outcome Measures in Rheumatology Arthritis Clinical Trials-Osteoarthritis Reseach Society International
PD	pharmacodynamics
PGA	patient global assessment
██████████	██████████
PK	pharmacokinetics
PR	pulse rate
PT	MedDRA preferred term
Q4W	every 4 weeks
Q8W	every 8 weeks

QOL	quality of life
RAND	all subjects randomized population
SAE	serious adverse event
SAF	safety analysis set
SAP	statistical analysis plan
SBP	systolic blood pressure
SC	subcutaneous
SD	standard deviation
SF-36	Short Form 36-item health survey
SIF	Subchondral insufficiency fracture
SOC	system organ class
TEAE	treatment emergent adverse event
TESAE	treatment emergent serious adverse events
[REDACTED]	[REDACTED]
ULN	upper limit of normal range
WHO	World Health Organization
WOMAC	Western Ontario and McMaster Osteoarthritis Index

1. INTRODUCTION

This statistical analysis plan (SAP) is based on the final protocol (v4.0) dated 31-July-2018. This protocol will plan to respectively perform the statistical analysis for the clinical trial data from screening to Week 16, from screening to Week 24 and from screening to Week 68.

For the clinical trial data from screening to Week 68, this SAP covers statistical analysis, tabulations and listings of the study data to investigate the efficacy and safety of MT-5547 SC 1mg q4w and 1mg q8w compared to matching placebo. Therefore, this SAP will be finalized prior to database lock at Week 68 to ensure the credibility of the study results by pre-specifying the statistical methods for the data analyses before un-blinding of treatment assignments. For the clinical trial data from screening to Week 16 and from screening to Week 24 was separately created.

Any statistical analysis details described in this document supersede any description of statistical analysis in the protocol.

2. STUDY OBJECTIVE AND ENDPOINTS

2.1. Study Objective(s)

The objective of this study is to verify the superiority of 16 weeks of MT-5547 treatment to placebo, as evidenced by the WOMAC pain subscale score (the efficacy outcome measure), in patients with osteoarthritis of the knee or hip. Additional objectives of the study are to investigate the efficacy, safety, and pharmacokinetics of MT-5547 in long-term use.

2.2. Study Endpoint(s)

2.2.1. Efficacy Endpoint(s)

- (1) Primary efficacy endpoint
WOMAC pain subscale score (change from baseline at Week 16)
- (2) Key secondary efficacy endpoint
WOMAC physical function subscale score (change from baseline at Week 16)
- (3) Secondary efficacy endpoints
 - 1) Patient global assessment (PGA) (change from baseline at each assessment time point)
 - 2) WOMAC pain subscale score (change from baseline at each assessment time point)
 - 3) WOMAC physical function subscale score (change from baseline at each assessment time point)
 - 4) WOMAC stiffness subscale score (change from baseline at each assessment time point)
 - 5) WOMAC total score (change from baseline at each assessment time point)
 - 6) Proportions of subjects with 30%, 50%, 70% and 90% improvements in their WOMAC pain subscale scores compared to baseline (at each assessment time point)

- 7) Proportions of subjects with 30%, 50%, 70% and 90% improvements in their WOMAC physical function subscale scores compared to baseline (at each assessment time point)
- 8) Proportions of subjects with 30%, 50% and 70% improvements in their PGA compared to baseline (at each assessment time point)
- 9) Numerical Rating Scale (NRS) score for the mean pain on walking in the evaluated joint (change from baseline at each assessment time point)
- 10) SF-36 (change from baseline at each assessment time point)
- 11) EQ-5D-5L (change from baseline at each assessment time point)
- 12) Improvement rate based on the Outcome Measures in Rheumatology Arthritis Clinical Trials-Osteoarthritis Research Society International (OMERACT-OARSI) criteria (at each assessment time point)
- 13) Amount of rescue medication used (number of days on which rescue medication was used, and amount [number of tablets] used)

2.2.2. Safety Assessment(s)

- (1) Adverse events and adverse reactions (clinically significant adverse events were identified as being adjudicated arthropathy, sympathetic nervous system disorders and altered peripheral sensation)
- (2) General clinical laboratory tests
- (3) Body weight
- (4) Vital signs
- (5) ECG
- (6) Physical examination
- (7) Joint pain questionnaire
- (8) Survey of autonomic symptoms
- (9) Assessment of orthostatic blood pressure
- (10) Neurological assessments
- (11) Bone density
- (12) Imaging Tests
- (13) Injection site assessments
- (14) Assessments of subjects undergoing joint replacement

2.2.3. Pharmacokinetics Assessment(s)

MT-5547 concentration in serum

Anti-MT-5547 antibody in serum

2.2.4. Pharmacodynamics Endpoint(s)

Efficacy: WOMAC pain subscale score, WOMAC physical function subscale score, PGA

Safety: alkaline phosphatase (ALP), C-reactive protein (CRP), bone specific alkaline phosphatase (BAP)

[figure not shown]
3. STUDY DESIGN

3.1. Study Design

Study Phase: Phase 2/3

Type of Study: Confirmatory Study

Parallel group, randomized, placebo-controlled, double-blind (24 weeks), multicenter

- 1) The post-treatment observation period will be the 20 weeks from the day after the end of the 48-week treatment period. Furthermore, for subjects discontinued from the study, the post-treatment observation period will be the 24 weeks from the administration of MT-5547 or MT-5547 placebo. If a joint replacement procedure is going to be performed, the postoperative test observation period will be the period from the day after the day of discontinuation until 20 weeks after the joint replacement procedure is performed.
- 2) From Week 16 to Week 48, the placebo group will receive an additional dose of naproxen tablets to reduce the dropout rate in the placebo group. The MT-5547 group will receive an additional dose of naproxen placebo tablets.
For each subject, the data for up through Week 16 will be fixed prior to the Week 20 visit, and the fixed data will be prepared.
- 3) The blind will be maintained, including for the study sponsor, until the key code is opened after the data have been fixed for all subjects in Week 24. In addition, in order to eliminate any bias that could affect the study assessments, to the extent possible, the blind will be maintained with respect to the study site and the subject even after the opening of the study sponsor key code.

3.2. Schedule of Study Procedures

3.2.1. Test/Observation Schedule

Statistical Analysis Plan
Protocol No. MT-5547-101
(1) Test/Observation Schedule from informed consent to Week 48 of treatment period (if a joint replacement procedure is not going to be performed)

Mitsubishi Tanabe Pharma Corporation
Treatment period

	Inform ed	Screening o observation period	Treatment period												At withdrawal ¹⁴		
			Day 1 Baseline	Week 1	Week 2	Week 4	Week 8	Week 12	Week 16	Week 20	Week 24	Week 28	Week 32	Week 36	Week 40	Week 44	Week 48
Visit times (visit window) ¹		Day -37 (~3) Day -7 (~1)															
Visit Number	1	2	3	4	5	6	7	8	9	10	11	12	13	14	15	16	17
Written informed consent	X	X	X	X													
Eligibility confirmed																	
Demographics	X	X	X	X													
Randomization ²				X													
Study drug/SC administration ³				X													
Administration of impurezen																	
Delivery of impurezen																	
Returns of impurezen																	
Delivery of acetaminophen																	
Return of acetaminophen/check of amount taken ³																	
Concomitant medications	X	X	X	X	X	X	X	X	X	X	X	X	X	X	X	X	X
[Efficacy]																	
NRS average daily pain ⁴				X													
WOMAC ²	X	X	X	X	X	X	X	X	X	X	X	X	X	X	X	X	X
FGA of OR	X	X	X	X	X	X	X	X	X	X	X	X	X	X	X	X	X
SP36																	
EQ-5D-5L																	
[Safety]																	
Body weight (height only at screening)	X																
Vital signs ⁵	X	X	X	X	X	X	X	X	X	X	X	X	X	X	X	X	X
ECG	X																
Physical examination	X	X	X	X	X	X	X	X	X	X	X	X	X	X	X	X	X
Orthostatic blood pressure																	
Injection site assessment (30 minutes after administration)																	
Joint Pain Questionnaire	X	X	X	X	X	X	X	X	X	X	X	X	X	X	X	X	X
Autonomic Nerve Questionnaire	X	X	X	X	X	X	X	X	X	X	X	X	X	X	X	X	X
Neurological evaluation	X	(brief version)	(brief version)	(brief version)	(brief version)	(brief version)	(brief version)	(brief version)	(brief version)	(brief version)	(brief version)	(brief version)	(brief version)	(brief version)	(brief version)	(brief version)	X
Radiology (bilateral knees, hips, shoulder) ⁷	X																
MRI testing (evaluated joint, contralateral joint, knee or hip joints with Ks 2,3) ⁷	X																
MRI testing (Joint of joint replacement super.)																	
Adverse events																	
At least pain worsening (image X-ray, MRI assessment) ⁸																	
JOA Score ⁹																	
Laboratory testing ¹⁰	X	X	X	X	X	X	X	X	X	X	X	X	X	X	X	X	X
Pregnancy test (ferr WOCGBP) ¹¹	X																
Bone density ¹²	X	X	X	X	X	X	X	X	X	X	X	X	X	X	X	X	X
[Urinalysis]																	
[Pharmacokinetics]																	
PK measurement		X ¹³	X	X	X ¹⁴	X ¹⁵	X ¹⁶	X ¹⁷	X ¹⁸	X ¹⁹	X ²⁰	X ²¹	X ²²	X ²³	X ²⁴	X ²⁵	X ²⁶
ADA antibody		X ²⁷															
[Other]																	

Confidential

(2) Test/Observation Schedule of post-treatment observation period (if a joint replacement procedure is not going to be performed)

	Post-treatment observation period (20 weeks) ¹⁴					
	Week 52	Week 56	Week 60	Week 64	Week 68	At withdrawal
Visit times (visit window)	Day 365 (± 7)	Day 393 (± 7)	Day 421 (± 7)	Day 449 (± 7)	Day 477 (± 7)	
Visit Number	18	19	20	21	22	
Written informed consent						
Eligibility confirmed						
Demographics						
Randomization ¹						
Study drug SC administration ²						
Administration of naproxen						
Delivery of naproxen						
Return of naproxen						
Delivery of acetaminophen						
Return of acetaminophen/check of amount taken ³						
Concomitant medications	X	X	X	X	X	X
[Efficacy]						
NRS (average daily pain) ⁴						
WOMAC ⁵	X		X		X	X
PGA of OA	X		X		X	X
SF-36					X	X
EQ-5D-5L					X	X
[Safety]						
Body weight (height: only at screening)					X	X
Vital signs ⁶	X				X	X
ECG						
Physical examination					X	X
Orthostatic blood pressure	X				X	X
Injection site assessment (30 minutes after administration)						
Joint Pain Questionnaire	X				X	X
Autonomic Nerve Questionnaire	X				X	X
	X					
Neurological evaluation	(brief version)				X	X
Radiology (bilateral knees, hips, shoulders) ⁷					X	X
MRI testing (evaluated joint, contralateral joint, knee or hip joints with K-L ≥ 3) ⁷						
MRI testing (joint of joint replacement surgery)						X
Adverse events	<					> X
At joint pain worsening (imaging [X-ray, MRI] assessments) ⁸	<					> X
JOA Score ⁹						X
Laboratory testing ¹⁰					X	X
Pregnancy test (for WOCBP) ¹¹	X				X	X
Bone density ¹²						
Urinalysis					X	X
[Pharmacokinetics]						
PK measurements	X	X			X	X
ADA antibody					X	X
[Other]						

- 1) Patients will be randomized (enrolled at the start of the treatment period) after all of the assessments through the pre-treatment observation period have been completed.
- 2) Investigational drug or comparative drug will be administered subcutaneously after all of the safety assessments, efficacy assessments, and collection of blood samples for pharmacokinetic assessments have been completed, and patients will be kept under supervision at the study site for 30 minutes after the administration of the study drug or comparative drug.
- 3) The dose of acetaminophen taken will be checked based on the treatment diary. Every night, patients will record in their treatment diaries the amount (number of tablets) of acetaminophen they took that day.
- 4) Every night (and as a rule at the same time) from the start of the pre-treatment observation period until the day before Week 16, patients will use the IVRS to report the mean pain on walking for the previous 24 hours (NRS data). Patients will receive instruction in how to use the IVRS on the day of the visit at the start of the pre-treatment observation period.
- 5) The WOMAC score at screening will be assessed for the right knee joint, the left knee joint, the right hip joint, and the left hip joint, and the index joint will be determined based on the WOMAC pain subscale scores. At the other time points, the WOMAC score will be assessed for the index joint only.
- 6) If the pulse is less than 45 bpm at an assessment time point after investigational drug or comparative drug administration, electrocardiography will be performed and the patient carefully examined for cardiac function abnormalities.

7) Screening:

The following imaging tests will be performed for patients who meet the study eligibility criteria, and the images will be submitted to a central adjudication office. Imaging tests will also be performed if the central adjudication office requests that additional tests be conducted.

- X-ray tests: Both knee joints, both hip joints, both shoulder joints
- MRI tests: The index joint, the joint opposite the index joint, and any knee or hip joints with a K-L grade of 3 or more MRI tests will be performed as needed by the (sub) investigator.

A check will be performed by the day specified below to make sure that the results of the central assessments meet the study enrollment criteria.

- X-ray tests: By the start of the pre-treatment observation period
- MRI tests: By baseline

If the results of the central assessments cannot be confirmed by the specified day, then re-screening will be performed.

After baseline:

At week 16, 48 (or at discontinuation of the treatment period) and at 68 weeks (or at the early discontinuation of the post-treatment observation period), images will be submitted to the central adjudication office. If the (sub) investigator determine that there is an abnormal finding compared to normal osteoarthritis, MRI tests will be performed as needed. The images will be submitted to a central adjudication office. Imaging tests will also be performed if the central adjudication office requests that additional tests be conducted, and the images submitted to the central adjudication office (for more detailed information, see in the text “9.2.4.1.11 Imaging Tests”).

Week 16:

The X-ray tests (both knee joints, both hip joints, both shoulder joints) will be performed by the (sub) investigator. The images will be submitted to a central adjudication office. The (sub) investigator will check the X-ray images before administered the investigational drug or comparative drug to determine whether or not investigational drug or comparative drug should be administered. If any abnormalities are found, investigational drug or comparative drug administration will be postponed. If the central adjudication office rules out adjudicated arthropathy, investigational drug or comparative drug administration will be resumed.

At discontinuation of the treatment period and discontinuation of the post-treatment observation period

The X-ray tests (both knee joints, both hip joints, both shoulder joints) will be performed by the (sub) investigator. The images will be submitted to a central adjudication office. If more than 30 days have passed since the last images were taken, images will be taken again. If not more than 30 days have passed, imaging tests will be performed if the (sub) investigator determines that it is necessary.

If joint replacement surgery is required, the MRI tests of the joint of surgery will be performed (for more detailed information, see in the text “9.2.4.1.13 Post-joint Replacement Procedure Assessment”).

- 8) If a patient experiences a sudden worsening of pain that would not occur in the normal course of osteoarthritis, the (sub) investigator will postpone investigational drug or comparative drug administration, and perform imaging test (X-ray and MRI) of the affected joint. Imaging test (X-ray and MRI) of other joints will be performed as needed by the

(sub) investigator. Imaging tests will also be performed if the central adjudication office requests that additional tests be conducted. All images will be submitted to the central adjudication office. The results of the central assessment will be checked by the (sub) investigator. The investigational drug or comparative drug administration will be postponed until the central adjudication office rules out adjudicated arthropathy. If adjudicated arthropathy is ruled out by the central assessment, then study treatment will be resumed. If the result of the central assessment is adjudicated arthropathy, then study treatment must be discontinued.

9) Assessments of the joint by JOA score at discontinuation will be performed for patients who required joint replacement surgery during the study.

10) Hematology and blood biochemistry tests will be performed. HbA1c, HBs antigen, HBs antibody, HCV antibody, and HIV antibody will be measured only at screening.

11) At screening, the pregnancy test will be performed using serum. At all other time points, the pregnancy test will be performed using urine. Furthermore, pregnancy tests will not be performed for postmenopausal females who have been amenorrheic for at least 1 year or for females who have undergone a surgical hysterectomy or bilateral ovariectomy. If a positive result is obtained on a urine pregnancy test, a serum pregnancy test will be performed. If a negative result is obtained on a serum pregnancy test, the study can be continued for the patient. If the serum pregnancy test is also positive, study treatment will be discontinued.

12) Bone density will be measured only at those study sites that are capable of performing measurements using the DEXA method. If it can not be measured at screening period, it may be measured during the pre-treatment observation period.

13) [REDACTED]

14) The Week 64 assessments may be performed by telephone.

15) The blood samples will be collected before the investigational drug or comparative drug is administered.

16) If a subject discontinues during the treatment period, a post-treatment observations will be performed at 4, 8, 12, 16, 20 and 24 weeks after the administration of the last dose of the investigational drug or control drug for the same parameters as those evaluated at the corresponding visits for completers. However, blood sample collection for pharmacokinetic evaluation is performed only 24 weeks after the last dose (blood sample collection for PK measurement is not necessary 4, 8 and 12 weeks after the last dose, which correspond to Weeks 48, 52 and 56 of the treatment period, respectively, for completers). The allowable time window for each evaluation time point is plus or minus 7 days.

The assessments at 12, and 20 weeks after the last dose administered to subjects discontinuing in the treatment period may be performed by telephone.

If the day of discontinuation from the treatment period and the day of discontinuation from the post-treatment observation period are the same (if the patient discontinued from the treatment period without proceeding to the post-treatment observation period), the assessments that are to be performed at discontinuation from the treatment period will be performed.

Discontinuation from the treatment period	4 weeks after the last dose	8 weeks after the last dose	12 weeks after the last dose	16 weeks after the last dose	20 weeks after the last dose	24 weeks after the last dose	Discontinuation from the post-treatment observation period
Completed of the treatment period	Week 48	Week 52	Week 56	Week 60	Week 64	Week 68	Discontinuation from the post-treatment observation period

If the assessments at discontinuation are included in the allowable time window for each assessment time point, the parameters that are to be assessed at discontinuation will be assessed. Subsequently, at each time point after the last dose, the corresponding post-treatment assessments will be performed.

If not more than 30 days have passed since the last images were taken, imaging will not have to be performed again, but may be performed if the (sub) investigator determines that it is necessary. The tests at discontinuation and post-joint replacement procedure test/observation will be performed for patients who required joint replacement surgery during the study. Imaging test (X-ray and MRI) will be submitted to a central adjudication office (for more detailed information, see "9.1.1 (3) Post-joint replacement procedure test/observation schedule). If the assessments at discontinuation are not performed before the joint replacement procedure is performed, then images from before the procedure will be obtained and sent to the central adjudication office.

17) The screening period is from "the screening start date" to the day before "the pre-treatment observation period start date," and the screening start date and end date are defined to be consistent with the allowable time window of "the pre-

treatment observation period" (for example, if the pre-treatment observation period is 4 days, the maximum screening period is the 30 days from Day-34 to Day-5, and if the pre-treatment observation period is 10 days, the maximum screening period is the 30 days from Day-40 to Day-11).

At each study visit after the baseline date, the assessments that are performed by the patients themselves (WOMAC, PGA, joint pain questionnaire, SF-36, EQ-5D-5L, survey of autonomic symptoms) will be performed before all of the other assessments (including the assessments that are performed by the (sub) investigator) (except for cases where imaging tests are performed on a different day).

(3) Post-joint replacement procedure test/observation schedule

Follow-up day (visit window)	After surgery ¹	Long-term ¹
	Follow-up survey, 4 weeks post-operative	Follow-up survey 2, 20 weeks post-operative
	29 days post-operative (± 5 days)	141 days post-operative (± 7 days)
Concomitant medications	X	X
[Safety]		
Vital signs	X	X
Joint Pain Questionnaire	X	X
JOA score²	X	X
Radiology (bilateral knees, hips, shoulders)	X	X
Adverse events	<----->	<----->
At joint pain worsening (imaging [X-ray, MRI] assessments)³	<----->	<----->

- 1) Information about the procedure, including prosthesis replacement and/or the extent of surgery wound healing, will be collected.
- 2) The condition of the joint following joint replacement surgery will be assessed using the JOA Score.
